15. STUDY ORGANISATIONAL STRUCTURE

15.1 Sponsor

The study is sponsored by the University of Birmingham.

15.2 Coordinating Centre

The study is being conducted under the auspices of the CRCTU, University of Birmingham according to their local procedures.

15.3 Trial Management Group

The Chief Investigator, Co-investigators including the Trial Statistician, Trial Manager and Trial Coordinator and patient advocate will form the Trial Management Group (TMG). The TMG will be responsible for the day-to-day conduct of the study, meeting at regular intervals, usually be teleconference. They will be responsible for the set-up, promotion, on-going management of the study, the interpretation of the results and preparation and presentation of relevant publications.

15.4 Trial Steering Committee

The Trial Steering Committee (TSC) will be set up with an independent chairperson to oversee the study. Membership will be composed of selected TMG members, independent clinicians and at least one patient advocate. The TSC will meet shortly before commencement of the study and at least once

a year (usually by teleconference), the meetings will usually be arranged to coincide with study milestones. The TSC will supervise the conduct of the study, monitoring progress including recruitment, data completeness, losses to follow-up, and deviations from the protocol. They will make recommendations about conduct and continuation of the study.

15.5 Data Monitoring Committee

Data analyses will be supplied in confidence to an independent Data Monitoring Committee (DMC). which will be asked to give advice on whether the accumulated data from the study, together with the results from other relevant research, justifies the continuing recruitment of further patients. The DMC will operate in accordance with a study specific charter based upon the template created by the Damocles Group. The DMC will is scheduled to meet at least one year after the study opens to recruitment and then annually thereafter until the study closes to recruitment, the meetings will usually be arranged to coincide with study milestones. Additional meetings may be called if recruitment is much faster than anticipated and the DMC may, at their discretion, request to meet more frequently or continue to meet following completion of recruitment. An emergency meeting may also be convened if a safety issue is identified. The DMC will report directly to the Trial Management Group who will convey the findings of the DMC to the Trial Steering Committee. The DMC may consider recommending the discontinuation of the study if the recruitment rate or data quality are unacceptable or if any issues are identified which may compromise patient safety.

15.6 Finance

This is a clinician-initiated and clinician-led research study funded by the National Institute for Health Research Health Technology Assessment (NIHR HTA) programme.

No individual per patient payment will be made to NHS Trusts, Investigators or patients.

16. ETHICAL CONSIDERATIONS

The study will be performed in accordance with the recommendations guiding physicians in biomedical research involving human subjects, adopted by the 18th World Medical Association General Assembly, Helsinki, Finland, 1964, amended by the 48th WMA General Assembly, Somerset West, Republic of South Africa, 1996 (website: http://www.wma.net/en/30publications/10policies/b3/index.html).

The study will be conducted in accordance with the Research Governance Framework for Health and Social Care, the applicable UK Statutory Instruments, (which include the Data Protection Act 1998 and Human Tissue Act 2004) and Good Clinical Practice (GCP). The protocol will be submitted to and approved by the main Research Ethics Committee (REC) prior to circulation.

Before any patients are enrolled into the study, the Principal Investigator at each site is required to obtain local Research & Development (R&D) approval. Sites will not be permitted to enrol patients until written confirmation of R&D approval is received by the Study Office.

It is the responsibility of the Principal Investigator to ensure that all subsequent amendments gain the necessary local approval. This does not affect the individual clinicians' responsibility to take immediate action if thought necessary to protect the health and interest of individual patients.

17. CONFIDENTIALITY AND DATA PROTECTION

Data Protection

Personal data recorded on all documents will be regarded as strictly confidential and will be handled and stored in accordance with the Data Protection Act 1998. We will seek consent to access electronic records relating to the patient held within the NHS. These may include (but are not limited to), Hospital Episode Statistics (HES), radiotherapy records, electronic chemotherapy records, electronic GP records, other data held by Cancer Intelligence Units or the Registrar of Births Marriages and Deaths. The intent is to link the clinical study data to relevant data within these other databases in order to prepopulate the case record forms. The initial feasibility stage will identify which data items provide maximum utility for the study purposes. This will allow data collection to, as far as possible, utilise routinely collected data, removing the need for costly research nurse and data manager time. It will also ensure timeliness and accuracy of study data. For example, all UK Radiotherapy Departments use electronic treat and verify systems. Directly using these systems to produce a record of radiotherapy received for bladder cancer will thus be both timely and accurate as it will be the definitive record of treatment received. Similar considerations apply to chemotherapy systems and HES in relation to surgery, including cystoscopy. We believe the "real-time" use of these data can

revolutionise study data collection, improving accuracy, increasing speed of collection and reducing costs. The study budget includes support for a statistician embedded within the informatics department at University Hospitals Birmingham NHS Foundation Trust (UHB) which has particular expertise in this area. This is a different approach to data collection to those usually employed, pilot studies carried out within UHB strongly support the potential utility of these methods. The principal barrier to these methods in the past has been consent to data sharing, hence this will be explicitly sought at study entry. Data linkage of this sort will be carried out within the NHS in the Informatics Department at UHB using pre-existing Information Governance procedures. As the HES data in particular is one of the main drivers of NHS funding, we will be using this to provide additional outcomes data for the health economics outcomes analysis. Data transferred to the CRCTU will be identified solely by a study number to ensure confidentiality.

The study will make extensive use of pre-existing NHS data to populate the case record forms. Care will be taken to restrict access to items strictly relevant to the study conduct.

With the patient's consent, their full name, gender, date of birth, NHS number, or in Scotland the Community Health Index (CHI), hospital number will be collected at study entry to allow tracing through Hospital Episode Statistics (HES), Cancer Registries, Cancer Intelligence Unit, NHS digital and other similar data sources kept by the NHS or related organisations if necessary.

Patients will be identified using only their unique trial number, initials and date of birth on the Case Report Form and correspondence between the Study Office and the participating site. However patients are asked to give permission for the Study Office to be sent a copy of their signed Informed Consent Form which will not be anonymised. This will be used to perform in-house monitoring of the consent process. The Investigator must maintain documents not for submission to the Study Office (e.g. Patient Identification Logs) in strict confidence. In the case of specific issues and/or queries from the regulatory authorities, it will be necessary to have access to the complete study records, provided that patient confidentiality is protected.

The Study Office will maintain the confidentiality of all patients' data and will not disclose information by which patients may be identified to any third party other than those directly involved in the treatment of the patient and organisations for which the patient has given explicit consent for data transfer (Cancer Registries, laboratory staff). Representatives of the BladderPath study team may be required to have access to patient's notes for quality assurance purposes but patients should be reassured that their confidentiality will be respected at all times.

Patient and Public Involvement (PPI)

The concept of the study is supported by the NCRI Bladder Clinical Studies Group (CSG). The CSG has two patient advocates who have participated in the study discussions at the Bladder CSG meetings; the BladderPath study has three patient advocates as members of either the Trial Management Group or Trial Steering Committee. The patient advocates have been involved in the review of the study design from a patient perspective and have helped with the design of the recruitment process and patient information sheet. A study website will be established and information about the study presented in lay and professional formats.

18. INSURANCE AND INDEMNITY

University of Birmingham employees are indemnified by the University insurers for negligent harm caused by the design or co-ordination of the clinical trials they undertake whilst in the University's employment.

In terms of liability at a site, NHS Trust and non-Trust hospitals have a duty to care for patients treated, whether or not the patient is taking part in a clinical trial. Compensation is therefore available via NHS indemnity in the event of clinical negligence having been proven.

The University of Birmingham cannot offer indemnity for non-negligent harm. The University of Birmingham is independent of any pharmaceutical company, and as such it is not covered by the Association of the British Pharmaceutical Industry (ABPI) guidelines for patient compensation.

19. PUBLICATION POLICY

Results of this study will be submitted for publication in a peer reviewed journal. The manuscript will be prepared by the Trial Management Group (TMG) and authorship will be determined by mutual agreement.

Any secondary publications and presentations prepared by Investigators must be reviewed by the TMG. Manuscripts must be submitted to the TMG in a timely fashion and in advance of being submitted for publication, to allow time for review and resolution of any outstanding issues. Authors must acknowledge that the study was performed with the support of the University of Birmingham. Intellectual property rights will be addressed in the Clinical Study Site Agreement between Sponsor and site.

APPENDIX 1 - WORLD MEDICAL ASSOCIATION DECLARATION OF HELSINKI

Recommendations guiding physicians in biomedical research involving human patients

Adopted by the 18th World Medical Assembly Helsinki, Finland, June 1964 and amended by the 29th World Medical Assembly, Tokyo, Japan, October 1975 35th World Medical Assembly, Venice, Italy, October 1983 41st World Medical Assembly, Hong Kong, September 1989 48th General Assembly, Somerset West, Republic of South Africa, October 1996

Introduction

It is the mission of the physician to safeguard the health of the people. His or her knowledge and conscience are dedicated to the fulfilment of this mission.

The Declaration of Geneva of the World Medical Association binds the physician with the words, "The Health of my patient will be my first consideration," and the International Code of Medical Ethics declares that, "A physician shall act only in the patient's interest when providing medical care which might have the effect of weakening the physical and mental condition of the patient."

The purpose of biomedical research involving human patients must be to improve diagnostic, therapeutic and prophylactic procedures and the understanding of the aetiology and pathogenesis of disease.

In current medical practice most diagnostic, therapeutic or prophylactic procedures involve hazards. This applies especially to biomedical research.

Medical progress is based on research which ultimately must rest in part on experimentation involving human patients.

In the field of biomedical research a fundamental distinction must be recognized between medical research in which the aim is essentially diagnostic or therapeutic for a patient, and medical research, the essential object of which is purely scientific and without implying direct diagnostic or therapeutic value to the person patiented to the research.

Special caution must be exercised in the conduct of research which may affect the environment, and the welfare of animals used for research must be respected.

Because it is essential that the results of laboratory experiments be applied to human beings to further scientific knowledge and to help suffering humanity, the World Medical Association has prepared the following recommendations as a guide to every physician in biomedical research involving human patients. They should be kept under review in the future. It must be stressed that the standards as drafted are only a guide to physicians all over the world. Physicians are not relieved from criminal, civil and ethical responsibilities under the laws of their own countries.

I. Basic principles

- 1. Biomedical research involving human patients must conform to generally accepted scientific principles and should be based on adequately performed laboratory and animal experimentation and on a thorough knowledge of the scientific literature.
- 2. The design and performance of each experimental procedure involving human patients should be clearly formulated in an experimental protocol which should be transmitted for consideration, comment and guidance to a specially appointed committee independent of the investigator and the sponsor provided that this independent committee is in conformity with the laws and regulations of the country in which the research experiment is performed.
- 3. Biomedical research involving human patients should be conducted only by scientifically qualified persons and under the supervision of a clinically competent medical person. The

responsibility for the human patient must always rest with a medically qualified person and never rest on the patient of the research, even though the patient has given his or her consent.

- 4. Biomedical research involving human patients cannot legitimately be carried out unless the importance of the objective is in proportion to the inherent risk to the patient.
- Every biomedical research project involving human patients should be preceded by careful assessment of predictable risks in comparison with foreseeable benefits to the patient or to others. Concern for the interests of the patient must always prevail over the interests of science and society.
- 6. The right of the research patient to safeguard his or her integrity must always be respected. Every precaution should be taken to respect the privacy of the patient and to minimize the impact of the study on the patient's physical and mental integrity and on the personality of the patient.
- 7. Physicians should abstain from engaging in research projects involving human patients unless they are satisfied that the hazards involved are believed to be predictable. Physicians should cease any investigation if the hazards are found to outweigh the potential benefits.
- 8. In publication of the results of his or her research, the physician is obliged to preserve the accuracy of the results. Reports of experimentation not in accordance with the principles laid down in this Declaration should not be accepted for publication.
- 9. In any research on human beings, each potential patient must be adequately informed of the aims, methods, anticipated benefits and potential hazards of the study and the discomfort it may entail. He or she should be informed that he or she is at liberty to abstain from participation in the study and that he or she is free to withdraw his or her consent to participation at any time. The physician should then obtain the patient's freely-given informed consent, preferably in writing.
- 10. When obtaining informed consent for the research project the physician should be particularly cautious if the patient is in a dependent relationship to him or her or may consent under duress. In that case the informed consent should be obtained by a physician who is not engaged in the investigation and who is completely independent of this official relationship.
- 11. In case of legal incompetence, informed consent should be obtained from the legal guardian in accordance with national legislation. Where physical or mental incapacity makes it impossible to obtain informed consent, or when the patient is a minor, permission from the responsible relative replaces that of the patient in accordance with national legislation. Whenever the minor child is in fact able to give a consent, the minor's consent must be obtained in addition to the consent of the minor's legal guardian.
- 12. The research protocol should always contain a statement of the ethical considerations involved and should indicate that the principles enunciated in the present Declaration are complied with.

II. Medical research combined with professional care (Clinical Research)

- 1. In the treatment of the sick person, the physician must be free to use a new diagnostic and therapeutic measure, if in his or her judgement it offers hope of saving life, re-establishing health or alleviating suffering.
- 2. The potential benefits, hazards and discomfort of a new method should be weighed against the advantages of the best current diagnostic and therapeutic methods.

- 3. In any medical study, every patient including those of a control group, if any should be assured of the best proven diagnostic and therapeutic method. This does not exclude the use of inert placebo in studies where no proven diagnostic or therapeutic method exists.
- 4. The refusal of the patient to participate in a study must never interfere with the physicianpatient relationship.
- 5. If the physician considers it essential not to obtain informed consent, the specific reasons for this proposal should be stated in the experimental protocol for transmission to the independent committee (I, 2).
- 6. The physician can combine medical research with professional care, the objective being the acquisition of new medical knowledge, only to the extent that medical research is justified by its potential diagnostic or therapeutic value for the patient.

III. Non-therapeutic biomedical research involving human Patients (Non-Clinical Biomedical Research)

- 1. In the purely scientific application of medical research carried out on a human being, it is the duty of the physician to remain the protector of the life and health of that person on whom biomedical research is being carried out.
- 2. The patient should be volunteers either healthy persons or patients for whom the experimental design is not related to the patient's illness.
- 3. The investigator or the investigating team should discontinue the research if in his/her or their judgement it may, if continued, be harmful to the individual.
- 4. In research on man, the interest of science and society should never take precedence over considerations related to the wellbeing of the patient.

APPENDIX 2 - DEFINITION OF ADVERSE EVENTS

Adverse Event

Any untoward medical occurrence in a patient or clinical study subject participating in the study which does not necessarily have a causal relationship with the treatment received.

Comment:

An AE can therefore be any unfavourable and unintended sign (including abnormal laboratory findings), symptom or disease temporally associated with the use of a medicinal product, whether or not related to the medicinal product.

Related Event

An event which resulted from the administration of any of the research procedures.

Serious Adverse Event

An untoward occurrence that:

- Results in death
- Is life-threatening*
- Requires hospitalisation** or prolongation of existing hospitalisation
- Results in persistent or significant disability or incapacity
- · Consists of a congenital anomaly/ birth defect
- Or is otherwise considered medically significant by the Investigator***

Comments:

The term severe is often used to describe the intensity (severity) of a specific event. This is not the same as serious, which is based on patients/event outcome or action criteria.

* Life threatening in the definition of an SAE refers to an event in which the patient was at risk of death at the time of the event; it does not refer to an event that hypothetically might have caused death if it were more severe.

**Hospitalisation is defined as an unplanned, formal inpatient admission, even if the hospitalisation is a precautionary measure for continued observation. Thus hospitalisation for protocol treatment (e.g. line insertion), elective procedures (unless brought forward because of worsening symptoms) or for social reasons (e.g. respite care) are not regarded as an SAE.

*** Medical judgment should be exercised in deciding whether an AE is serious in other situations. Important AEs that are not immediately life threatening or do not result in death or hospitalisation but may jeopardise the subject or may require intervention to prevent one of the other outcomes listed in the definition above, should be considered serious.

Unexpected and Related Event

An event which meets the definition of both an Unexpected Event and a Related Event.

Unexpected Event

The type of event that is not listed in the protocol as an expected occurrence.

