From the above, it is clear that the main functions of TURBT in MIBC are diagnosis of cancer and staging. Diagnosis does not require large quantities of tissue – very small amounts are sufficient to confirm the presence of high grade malignant cells to ascertain grade (as exemplified by the almost ubiquitous use of urine cytology). The main function of TURBT in MIBC therefore is to assess stage. Where muscle is adequately sampled and is found to contain tumour, a diagnosis of MIBC is correct by definition (although not a more comprehensive nodal or metastasis stage). The issue is the under staging of high-grade tumours due to inadequate sampling of muscle that subsequently turns out to be involved. As cystectomy is a recognised treatment for high risk NMIBC, either at diagnosis or after treatment failure such as Bacillus Calmette-Guerin (BCG), the false negative rate with respect to distinguishing NMIBC from MIBC in the highest risk cases can be estimated - this appears to be as high as 30%^{3, 30}, though will clearly vary depending on operator. Within this context we can assess the accuracy of MRI for the same purpose. The key factor here is the split between tumours of stage pT1 and below versus pT2 and above.

Thus, the diagnostic function of TURBT can be substituted by a smaller biopsy obtained during flexible cystoscopy. For staging, MRI has performance characteristics that exceed those reported for TURBT, are less subject to operator variability, and are amenable to external review. In most cases, the therapeutic benefit for TURBT in MIBC patients remains unproven, particularly if cystectomy is the preferred definitive treatment option. The literature on staging bladder cancer has been recently reviewed by Bouchelouche and co-workers¹⁹. A role for TURBT as palliation of severe symptoms from MIBC pending a definitive treatment decision will remain. Its precise magnitude will be quantified in this study but is likely to be limited as, in most cases, symptoms such as haematuria are intermittent (one of the factors leading to delayed presentation).

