8.1 Reporting Requirements

8.1.1 Adverse Events

MRI and TURBT are both well documented and widely used procedures. As the safety profiles of both procedures are well characterised, only Serious Adverse Events (SAEs) experienced due to the procedures will be reported.

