8.1.2.1 Expected Serious Adverse Events

We are not expecting any SAEs to occur as a result of participation in this study.

Expected serious adverse events do not need to be reported to the study team.

The following are regarded as expected SAEs for the purpose of study and should not be reported on an SAE form:

- BladderPath
 - Anaemia
 - Bladder discomfort/pain
 - Bladder perforation
 - Bleeding resulting in clot retention
 - Constipation
 - Contrast reaction
 - Diarrhoea
 - Deep Vein Thrombosis (DVT)
 - Fever
 - Gout
 - Haematuria
 - SAEs that are thought to have occurred as a result of the patient's cancer treatment
 - SAEs that are related to symptoms or progression of the patient's cancer

- Insomnia
- Nausea
- Postoperative dysuria
- Prolonged catheterisation
- Skin rash
- Urethral stricture
- Urinary frequency
- Urinary retention
- Urinary tract infection
- Vomiting
- Increased white blood cell count
- SAEs that are related to a pre-existing condition
- Death from cancer, as a result of the patient's cancer treatment or from a preexisting medical condition

This is not an exclusive list and Investigators should only report SAEs which are attributable to the study protocol.

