8.2.2 Study Office

On receipt of an SAE Form seriousness and causality will be determined independently by a Clinical Coordinator. An SAE judged by the Investigator or Clinical Coordinator to have a reasonable causal relationship with the study treatment will be regarded as a related SAE. The Clinical Coordinator will also assess all related SAEs for expectedness. If the event is unexpected (i.e. is not defined in the protocol as an expected event) it will be classified as an unexpected and related SAE.

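### SAE reporting is built around the MRI scan rather than the image-directed pathway, so the SAE count and the DMC's SAE review would largely miss harm from omitting TURBT or acting on a wrong MRI

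*Protocol*

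**What the plan says.** The protocol describes the intervention in two ways. Section 7.7 calls it a diagnostic and staging pathway directed by imaging, while section 8.2 names MRI as the only intervention. Under section 7.2, pathway 2 patients with possible MIBC have mpMRI in place of TURBT.

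Four tests govern what is reported or counted as related:

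- Section 8.1.1: "only Serious Adverse Events (SAEs) experienced due to the procedures will be reported".
- Section 8.1.2.1: "Investigators should only report SAEs which are attributable to the study protocol".
- Section 8.2.2, once a form has arrived: an SAE judged by the investigator or the Clinical Coordinator to have a "reasonable causal relationship with the study treatment will be regarded as a related SAE".
- Appendix 2, for a related event: "An event which resulted from the administration of any of the research procedures".

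Section 8.1.2.1 also lists events that do not go on an SAE form. The list includes "SAEs that are thought to have occurred as a result of the patient's cancer treatment" and "SAEs that are related to symptoms or progression of the patient's cancer". It names haematuria, clot retention, urinary retention and anaemia separately.

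Table 2 makes the number of SAEs a secondary outcome of the final stage, and section 8.2.5 has the DMC review all SAEs. Section 1.2 says: "A role for TURBT as palliation of severe symptoms from MIBC pending a definitive treatment decision will remain". It adds that the study will measure the size of that role.

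**The concern.** Pathway 2 can do harm in ways that a scan cannot. A tumour left in place can bleed or obstruct while the patient waits. A wrong MRI read can send a patient without muscle invasion to radical treatment, or delay the right treatment. The reporting rules ask about complications of the MRI or TURBT and exempt most of what these other routes would produce.

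The SAE comparison and the DMC's SAE listing would then be weakest where the new pathway differs most from the old one. A reassuring SAE table could reflect the exemptions rather than the patients' experience.

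**Working it through.** **1. Two example events taken through the rules**

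| Step | A: pathway 2 patient with MIBC, unplanned admission with clot retention before treatment | B: NMIBC read as invasive on MRI, serious complication of chemotherapy or radiotherapy |
|---|---|---|
| Serious under Appendix 2? | Yes (unplanned admission) | Yes, if it meets a seriousness criterion |
| 8.1.1: due to MRI or TURBT? | No | No |
| 8.1.2.1: exempt? | Yes, twice (cancer symptoms; clot retention by name) | Yes (cancer treatment) |
| 8.2.2: causality test | Not reached, as no form is sent | Not reached |
| Appendix 2: related? | Not clearly; the scan did not cause it | Not clearly |
| 8.2.3.1: expedited to the REC? | No; a listed event is expected | No |

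The barrier is mainly sections 8.1.1 and 8.1.2.1. Rewording Appendix 2 alone would change neither column's outcome.

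Appendix 2 treats an admission for a procedure brought forward because symptoms worsened as potentially serious. Section 8.1.2.1 then exempts serious events related to cancer symptoms.

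**2. What other outcomes catch (Table 2 and section 13.1)**

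- Unnecessary cystectomy, staging error and delay to correct treatment are secondary outcomes of the final stage.
- Progression and death enter through CPFS, metastatic progression and survival.
- Symptom admissions before treatment are not a named outcome. CPFS does not count them. Time to definitive treatment ends at the first TURBT, so a palliative TURBT in pathway 2 would register as reaching treatment.
- Serious complications of chemotherapy or radiotherapy given on a wrong stage are not a named outcome. The cystectomy count does not include them.

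**3. Size**

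Inputs from the protocol: 950 patients (13.2), randomised 1:1 (6.1.2); about 50% possible MIBC (13.2.1); 20–25% MIBC and a planned pathway 2 median of 70 days to treatment (13.2.2); MRI specificity 100% (1.4). Assumptions: all MIBC patients fall in the possible MIBC group; specificity could be 90–95%; 5–15% of MIBC patients have an unplanned admission or brought-forward procedure for bladder symptoms while waiting.

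- Pathway 2: 950 / 2 = 475. Possible MIBC: 475 × 0.50 = 237.5, about 238.
- MIBC: 475 × 0.20 to 0.25 = 95 to 119.
- NMIBC whose treatment depends on the MRI: 237.5 minus 95 to 119 = 119 to 143.
- Misdirected patients: 0 at 100% specificity; × 0.05 = 6 to 7 at 95%; × 0.10 = 12 to 14 at 90%. These are patients exposed to the risk, not SAEs.
- Symptom events while waiting: 95 × 0.05 to 119 × 0.15 = 5 to 18.

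Under section 8.1.2.1, neither those symptom events nor serious events from the misdirected patients' cancer treatment need go on an SAE form.

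**The case against.** A reader might infer that such harm can never count as related. The protocol does not support that. Saying that an event resulted from a procedure does not exclude downstream causes. Section 8.2.2 tests for a reasonable causal link with the study treatment, section 8.1.2.1 speaks of attribution to the protocol, and section 7.7 makes the intervention a pathway, so an assessor could judge such an event related. However, the section 8.2.2 test applies only to forms received, and the attribution sentence limits reporting without overriding the list.

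A reader might also infer that the harm is absent from the safety data altogether, or that a finding of equal safety would follow from the definitions. That goes too far as well. The outcomes in part 2 of the working compare much of the harm by randomised arm, and section 14 collects inpatient stays from HES for the economic evaluation. The DMC sees accumulated data and not only SAEs (section 15.5). Section 8.2.3.2 requires immediate notice to the REC of any significant safety issue. Palliative TURBT can be counted from the TURBT Form, HES surgery data and treatment counts, so the SAE rules do not defeat that aim in section 1.2.

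The size is soft. At the protocol's own specificity nobody is misdirected, and the admission rate is assumed. Pathway 1 patients also wait with a tumour in place before TURBT, and no comparator is calculated for them. All of this stands. It narrows the point to SAE reporting and the two gaps named in the working.

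**Conclusion.** The point holds in this limited form. The relatedness and reportability tests are not reconciled with one another or with the two descriptions of the intervention. Together with the section 8.1.2.1 list, they mean that the SAE count and the DMC's SAE review would largely miss harm from omitting TURBT or acting on a wrong MRI. Other outcomes cover part of that harm. Two parts are left without a named outcome: symptom admissions before treatment, and serious complications of non-surgical treatment given on a wrong stage.

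On planning figures this might be 5 to 18 symptom events in pathway 2, plus serious events among 0 to 14 misdirected patients. These ranges rest on assumed admission rates (5–15%) and specificity (90–100%) and say nothing about a difference between arms. The primary analysis is unaffected. The change is worth making because it is cheap and bears directly on what the DMC can see.

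**What to change.** Amend the reporting wording, for both arms alike; patient management does not change.

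1. Reconcile sections 7.7, 8.1.1, 8.1.2.1, 8.2 and 8.2.2 with Appendix 2, with one description of the intervention and one test. Related should cover an event resulting from a study procedure, from treatment given, delayed or withheld because of its result, or from the omission of TURBT.
2. In section 8.1.2.1, state that none of the exemptions, including the named bleeding, retention and anaemia entries, applies to:
   - (i) serious events after radical treatment in patients whose final histology shows no muscle invasion;
   - (ii) unplanned admissions, or procedures brought forward, for bladder symptoms between randomisation and the first treatment after staging.
3. State whether these events also cease to be expected for REC reporting under section 8.2.3.1.
4. Report (i) and (ii) by randomised arm to the DMC and in the final report, using HES admissions for consenting patients. The length of window (ii) may differ by arm, so give the time at risk with the counts. Patients treated without surgery may lack histology to classify them under (i) and should be shown separately.

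Cost: a protocol amendment, somewhat more site reporting and a fuller SAE table. HES linkage is already planned, but it depends on consent and runs eight weeks behind (section 10.1), so it supports periodic review rather than immediate alerts.
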